who received lapatinib and 7% in those on placebo. Risks of adverse events are not additive or cumulative. SAEs were reported in 6% of those on lapatinib compared to 5% on placebo. Cardiac events including left ventricular ejection fraction decreases were reported in approximately 1% of patients and most have partial or full recovery. Symptomatic decreases in ejection fraction were observed in approximately 0.3% of patients on lapatinib. Interstitial lung disease is observed in 0.2% of patients. Hepatotoxicity has been observed in <1% of patients. Grade 3 and 4 diarrhea occurs in <10% of patients. Nausea may be seen in 18% of patients and rash in 29% (Investigators' Brochure).

2. Prior to initiating therapy, patients will undergo an echocardiogram and ECG to evaluate the ejection fraction, and the echocardiogram will be repeated every 8 weeks and on visit. Patients will be evaluated for adverse effects monthly with physical examinations, chemistry and hematology panels, and ECGs. Adverse events will be graded by the NCI-CTC. Common adverse events include: hand-foot syndrome, rash, diarrhea, indigestion, nausea, vomiting, anorexia, anemia, low platelets, abnormal liver tests (ALT (SGPT) level raised, AST/SGOT level raised, hyperbilirubinemia, backache, pain in limb, insomnia, fatigue, and shortness of breath. Rare but serious events include: heart failure (depression of left ventricular systolic function), abnormal heart beat (prolonged QT interval), liver damage (hepatotoxicity), and lung problems (interstitial lung disease/pneumonitis). Lapatinib will be discontinued in those who developed decreased ejection fraction, who develop pulmonary symptoms. Those subjects with toxicity less than or equal to Grade 2 on the NCI-CTC will have their dose held and resumed when the toxicity has resolved. Those subjects with toxicity equal to Grade 3 on the NCI-CTC will have their dose held and resumed at a fifty percent dose reduction when the toxicity has resolved. Those subjects with toxicity equal to Grade 4 on the NCI-CTC will be discontinued on the study drug. [name], from Oncology department at Cedars-Sinai Medical Center, will assist us in monitoring patients for adverse events.
3. If at any time a patient demonstrates a worsening of their visual fields or tumor growth on MRI, they will be withdrawn from the study and referred for surgery.
4. For further safety monitoring, subjects may be asked to have additional laboratory testing as deemed necessary by the investigators. This would require subjects to have extra blood draws which can also be done at outside laboratories.
5. A DSMB will be set up to monitor safety of the study at all trial sites.

Cardiac Events

Addition to SAE definition:

Cardiovascular events have been seen in 1.0% of subjects on lapatinib with or following anthracyclines, with symptomatic events in 0.3%. As a precaution, the following will be reported as an SAE:

- Cardiac dysfunction will be reported as an SAE and will be defined as any signs or symptoms of deterioration in left ventricular cardiac function that are Grade 3 (NCI CTCAE) or a $\geq 20\%$ decrease in left ventricular cardiac ejection fraction (LVEF) relative to baseline which is below the institution's lower limit of normal.

Refer to NCI CTCAE grading of left ventricular cardiac function.

Criteria for Evaluating Cardiac Events:

Asymptomatic cardiac events:

[figure not shown]
Subjects who have a $\geq 20\%$ decrease in LVEF relative to baseline, and the ejection fraction is below the institution's lower limit of normal, should have a repeat evaluation of ejection fraction 1-2 weeks later while still receiving investigational product.

- If the repeat ejection fraction evaluation confirms a $\geq 20\%$ decrease in LVEF, and the ejection fraction is below the institution's lower limit of normal, then investigational product should be temporarily discontinued.
- If the LVEF recovers during the next 3 weeks, after consultation and approval of the medical monitor, the subject may be restarted on investigational product at a reduced dose. For such subjects, monitoring of left ventricular ejection fraction will then be performed 2 weeks and 4 weeks after rechallenge, and then every 4 weeks thereafter.
- If repeat ejection fraction evaluation still shows a decrease $\geq 20\%$ in LVEF relative to baseline, and the value is below the institution's lower limit of normal, then the subject should be withdrawn from investigational product.

Symptomatic cardiac events:

Subjects with an NCI CTCAE grade 3 or 4 LVEF relative decrease must be withdrawn from study medication.

Figure 1 Algorithm for continuation and discontinuation of GW572016 (lapatinib) and/or trastuzumab based on interval LVEF assessments, for patients with NYHA class I or II congestive heart failure

Liver Chemistry Stopping Criteria

Overall, 45% of patients experience hepatic abnormalities on lapatinib and capecitabine. In a phase III trial of lapatinib monotherapy (n = 1573), 8% of patients experienced hepatobiliary events, 3% of those were SAEs. With lapatinib monotherapy, grade 3 hyperbilirubinemia has been reported in 2% of patients and grade 4 elevations in ALT/AST in 2%. Hepatotoxicity has been observed in <1% of subjects. Liver chemistry stopping and follow up criteria have been designed to assure subject safety and evaluate liver event etiology. All subjects who meet liver chemistry criteria requiring permanent discontinuation of investigational product must continue to be followed for the study assessments and procedures as defined in Section X and at the time points indicated in the Time & Events Table in Section X.

If a subject experiences ALT $>3 \times$ ULN and total bilirubin $>2.0 \times$ ULN ($>35\%$ direct; bilirubin fractionation required*), then the following actions must be taken:

immediately and permanently discontinue investigational product;
complete the SAE data collection tool, the liver event CRF, and the liver imaging and/or liver biopsy CRFs, if these tests are performed;
in addition to the liver event follow up assessments defined in Section X.X. below, the following are suggested: specialist or hepatology consultation; anti-nuclear antibody, anti-smooth muscle antibody, and Type 1 anti-liver kidney microsomal antibodies; and liver imaging and/or liver biopsy to evaluate liver disease;
promptly report the event to Novartis within 24 hours of learning its occurrence (refer to **'Reporting Serious Adverse Events section'** for guidance on prompt reporting to Novartis);
monitor every week until liver chemistries resolve, stabilize or return to within baseline values;
do not re-challenge with investigational product.

***NOTE:** bilirubin fractionation should be performed if testing is available. If testing is unavailable and a subject meets the criterion of total bilirubin $>2.0 \times$ ULN, then the aforementioned actions must still be performed.

If a subject experiences:

ALT $>8 \times$ ULN or
ALT $>5 \times$ ULN persisting for ≥ 2 weeks : retest within 3 days from the first occurrence and then weekly to determine if ALT elevation persists or
ALT $>3 \times$ ULN with signs or symptoms of hepatitis or hypersensitivity (the appearance or worsening of fatigue, nausea, vomiting, right upper quadrant pain or tenderness, fever, rash, or eosinophilia)

then hold investigational product for 2 weeks, repeat liver chemistry testing in 2 weeks, and then call the Novartis Medical Monitor to discuss the possibility of re-challenging with investigational product.

If the treatment is exhibiting efficacy **and** the subject wants to continue for potential benefit of lapatinib therapy after being informed of the results of liver chemistry testing,

then the investigational product may be re-started at the reduced dose agreed upon by the investigator and the Novartis Medical Monitor. In such cases, Study Visit #8 will not take place if the decision to continue on lapatinib takes place prior to discontinuation of study drug on study. Liver chemistries and aforementioned signs and symptoms should be monitored at a minimum of every 2 weeks until resolution, stabilization, or a return to baseline values, at which point monitoring should be continued per protocol.

If a subject experiences ALT $>3 \times$ ULN **but** $<5 \times$ ULN **and** total bilirubin $\leq 2 \times$ ULN, without signs or symptoms of hepatitis or hypersensitivity, **and** who can be monitored weekly, then the following actions should be taken:

continue investigational product;
monitor weekly until liver chemistries resolve, stabilize, or return to within baseline, then monitor liver chemistries as per protocol assessment schedule;
if ALT >3 and $< 5 \times$ ULN for > 4 weeks, discontinue the treatment;
if at any time this subject meets any of the aforementioned liver chemistry stopping criteria, then proceed as described above.

Liver Chemistry Follow up Criteria

For all subjects who meet any of the liver chemistry criteria described above, make every attempt to carry out the liver event follow up assessments described below:

Viral hepatitis serology including:

- Hepatitis A IgM antibody;
- Hepatitis B surface antigen and Hepatitis B Core Antibody (IgM);
- Hepatitis C RNA;
- Cytomegalovirus IgM antibody;
- Epstein-Barr viral capsid antigen IgM antibody (or if unavailable, obtain heterophile antibody or monospot testing);
- Hepatitis E IgM antibody (if subject resides or has traveled outside USA or Canada in past 3 months);

Serum creatine phosphokinase (CPK) and lactate dehydrogenase (LDH);

Complete blood count with differential to assess eosinophilia;

Record the appearance or worsening of clinical symptoms of hepatitis, or hypersensitivity, fatigue, decreased appetite, nausea, vomiting, abdominal pain, jaundice, fever, or rash as relevant on an AE report form;

Record use of concomitant medications, acetaminophen, herbal remedies, other over the counter medications, or putative hepatotoxins, on the concomitant medications report form;

Record alcohol use on the liver event alcohol intake case report form.

Refer to Appendix 3 for a liver safety algorithm detailing stopping and follow up criteria.

Safety

Add frequency of LFTs to Safety Assessment section and Time & Events Table as applicable:

- During treatment phase: every 4 - 6 weeks (to best fit protocol schedule) for duration of concurrent chemotherapy administration or for first 6 months, then

every 8 – 12 weeks (or more frequently, if clinically indicated) for remaining on treatment period

- During post-treatment phase: continue to monitor any liver chemistry abnormalities noted during treatment or within 30 days after last dose of investigational product until values return to normal or baseline (this language should be in protocols already)

In the Safety Assessment section, make a reference to section containing the Liver Chemistry Stopping and Follow up Criteria.

In the Laboratory Assessment section, mention that bilirubin fractionation is recommended if total bilirubin $>2 \times$ ULN when testing is available.

[figure not shown]
Hepatobiliary events have been seen in subjects taking lapatinib and other tyrosine kinase inhibitors. As a precaution, the following will be reported as an SAE:

- ALT $>3 \times$ ULN and total bilirubin $>2.0 \times$ ULN ($>35\%$ direct; bilirubin fractionation required).

NOTE: bilirubin fractionation should be performed if testing is available. If testing is unavailable and a subject meets the criterion of total bilirubin $>2.0 \times$ ULN, then the event should still be reported as an SAE.

Other hepatic events should be documented as an AE or an SAE as appropriate.

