Subjects with prolactinomas who are resistant to dopamine agonist therapy who manifest continued tumor size growth while on a dopamine agonist, unless intolerant of adequate doses of a dopamine agonist.

Subjects with malignant pituitary tumors will be eligible for the malignant pituitary tumor arm of the study regardless of existing visual deficits.

Exclusion criteria: Children will be excluded. If subjects have preexisting visual field deficits, they will be monitored on more frequent basis. Patients will also be excluded if they have left ventricular ejection fraction less than 50 %, moderate to severe hepatic impairment (see below for specifics), active hepatitis, HIV positivity, concurrent cancers, life expectancy less than one year, and pregnancy. Pregnant patients will be excluded. Childbearing age women will be required to use

contraception. Patients who become pregnant during the study should discontinue the study immediately.

Withdrawal of Subjects:

Monitoring for adverse effects: Prior to initiating therapy, patients will undergo an echocardiogram and ECG to evaluate the ejection fraction, and the echocardiogram will be repeated every 8 weeks (Visit 3, 5, and 7) and on visit 8. Patients will also undergo ophthalmic testing at visits 1, 4, and 7. Patients with pre-existing stable visual field compromise prior to enrollment will undergo visual field testing at visits 1, 2, and 3, and if stable, then they will proceed with visual field testing every three months for the duration of the study. Patients will be evaluated for adverse effects monthly with physical examinations, chemistry and hematology panels, and ECGs. Adverse events will be graded by the NCI-CTC and include: anorexia, decreased ejection fraction, interstitial lung disease/pneumonitis, diarrhea, nausea, vomiting, hepatotoxicity, rash, and fatigue. Lapatinib will be discontinued in those who developed decreased ejection fraction, who develop pulmonary symptoms, retinal toxicity, worsening of visual fields, and those with toxicity greater than or equal to Grade 2 on the NCI-CTC. [name], from Oncology department at Cedars-Sinai Medical Center, will assist us in monitoring patients for adverse events.

If at any time a patient demonstrates compromise of his visual fields, dilated retinal exam or tumor growth on MRI, he will be withdrawn from the study and referred for surgery.

Section 6.0 Treatment of Subjects

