Pregnancy Test for pre-menopausal women	X	X	X	X	X	X	X	X

^ Only for subjects with visual field deficits

^^ will be waived if subjects had MRI at outside hospital within 3 months of baseline visit

* Only for subjects with acromegaly from malignant tumors

+Only for subjects with ACTH secreting adenomas from malignant tumors

**Visit 8 is only required if stopping Lapatinib at visit 7. Patients continuing on Lapatinib after visit 7 will be followed by their physician as clinically appropriate.

Section 7.0 Assessment of Efficacy

a. Primary outcome variable.

Primary outcome in nonfunctioning pituitary adenomas: 40% reduction in tumor size in any dimension. Tumor size and volume will be calculated using Open Source OsiriX® Imaging Software for MacOS. MRIs will be performed at baseline and at 3 and 6 months All MRIs will be centrally read by the dedicated pituitary radiologist at CSMC.

Primary outcome in prolactinomas: 40% reduction in tumor size in any dimension.

Primary outcome in malignant pituitary tumors: Progression free survival

b. Secondary outcome variables.

Secondary outcomes in prolactinomas:

(a) achievement of 50% reduction of PRL levels (b) PRL normalization (c) percent reduction in PRL levels (d) percent reduction in tumor volume. Tumor volume will be calculated using Open Source OsiriX® Imaging Software for MacOS. (e) correlation of tumor size and PRL reduction (f) clinical predictors of TKI response, including age, gender, duration of disease, dose and duration of dopamine agonist therapy, baseline PRL, and baseline tumor size.

Secondary outcomes in malignant pituitary tumors: partial response, complete response, mortality, 24 hour urine free cortisol levels for Cushing carcinomas, IGF-1 levels for acromegaly carcinomas

We will correlate ErbB receptor expression with the subjects' clinical response to the study drug. This will be performed through immunohistochemistry staining of pituitary tumor slides from surgery.

Section 8.0 Assessment of Safety

1. *Monitoring for adverse effects (further detailed below):* Data has been collected on over 12000 subjects on combination therapy of lapatinib and other chemotherapies, and over 4000 subjects have been treated with lapatinib monotherapy, with 2347 of those specifically in breast cancer. With monotherapy, majority of AEs were Grade 1 or 2 in severity. The incidence of Grade 3 and Grade 4 events was 21% in those

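### For an asymptomatic LVEF fall that the protocol classes as an SAE, Section 5.0 and Section 8.0 item 2 stop lapatinib, while the cardiac criteria continue it until a retest 1–2 weeks later

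*Combined protocol and SAP*

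**What the plan says.** Section 5.0, Withdrawal of Subjects: "Lapatinib will be discontinued in those who developed decreased ejection fraction, who develop pulmonary symptoms, retinal toxicity, worsening of visual fields". The same sentence adds "those with toxicity greater than or equal to Grade 2 on the NCI-CTC". The scheduled checks are given as "the echocardiogram will be repeated every 8 weeks (Visit 3, 5, and 7) and on visit 8".

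Section 8.0, item 2: "Lapatinib will be discontinued in those who developed decreased ejection fraction, who develop pulmonary symptoms". For toxicities up to Grade 2, the same item uses different language: patients "will have their dose held and resumed when the toxicity has resolved".

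Section 8.0, Criteria for Evaluating Cardiac Events, sets a threshold for asymptomatic patients: a relative LVEF fall of at least 20% that also takes the value below the institution's lower limit of normal (LLN). The steps are a repeat test after 1–2 weeks with drug continuing, a temporary stop if the fall is confirmed, and a possible reduced-dose restart if LVEF recovers over the next 3 weeks and the medical monitor approves. Without recovery, the patient comes off drug. The Cardiac Events text makes the same threshold reportable as an SAE.

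**The concern.** A site that sees this echocardiogram result has two written instructions for that day's dose: stop, or carry on until the retest. Whichever it follows, it departs from the other. There are three sites, and they could act differently on an event the protocol treats as serious.

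Outside the malignant arm, Section 6.0 describes patients who would otherwise be observed with serial MRIs, so tolerance for avoidable cardiac exposure should be low. The medical monitor's approval applies to the restart, not to the interval before the retest. The DSMB monitors safety but does not tell a site which rule to apply.

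**Working it through.** The protocol states no figure to reproduce here, so the check sets the rules side by side for one patient.

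**Illustrative case (LVEF values assumed).** Baseline LVEF is 65% and the visit 3 value (day 60) is 48%, with no symptoms. Relative fall = (65 − 48)/65 = 17/65 = 26.2%, which exceeds 20%. The protocol gives no LLN (its entry cut-off is 50%), so I assume an LLN above 48%. The patient then meets the cardiac threshold and the SAE definition.

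| Stage | Section 5.0 and Section 8.0 item 2 | Cardiac criteria |
|---|---|---|
| Day of finding | Discontinue | Continue; retest in 1–2 weeks |
| Fall confirmed | Already off drug | Temporary stop |
| Recovery within 3 weeks | No restart provision | Reduced-dose restart if the medical monitor approves |
| No recovery | Off drug | Withdrawn from drug |

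The first row conflicts whether the general rule means a permanent or a temporary stop. Its length is 1–2 weeks, that is 7–14 days. The rules agree for symptomatic Grade 3 or 4 decreases, where the cardiac criteria also withdraw drug.

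**Does any text settle precedence?**
- Section 8.0 item 1 is headed "Monitoring for adverse effects (further detailed below". It introduces the safety section and does not mention Section 5.0's stop.
- Table 1 sends Grade 3–4 left ventricular dysfunction to a specific section. Its Cardiac row sends NYHA class I–II patients to the LVEF algorithm. That figure is not in the text available to me, and I do not count its absence as a gap.
- Dose Delays and Dose Reductions refers Grade 3–4 left ventricular dysfunction to the cardiac criteria.

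These suggest that the cardiac section is the operative detail. None amends the discontinuation sentences.

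**Frequency.** Section 8.0 item 1 gives cardiac events, including LVEF decreases, in about 1% of patients and says "Symptomatic decreases in ejection fraction were observed in approximately 0.3% of patients on lapatinib". The Cardiac Events text ties the 1.0% to use with or following anthracyclines. Taking the difference as asymptomatic (an assumption): 1.0% − 0.3% = 0.7%. With the planned 30 patients:
- expected number = 30 × 0.007 = 0.21; chance of at least one = 1 − 0.993^30 = 19.0%;
- if half reach the threshold (assumed, 0.35%): 30 × 0.0035 = 0.105; 1 − 0.9965^30 = 10.0%.

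The malignant arm has no stated size and is left out.

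**Two further checks that shape the remedy.**
- A fall from 55% to 47% is 8/55 = 14.5%. It is below the 50% entry cut-off but does not meet the cardiac threshold. Section 5.0 can be read to stop drug; the cardiac criteria prescribe nothing.
- The 3-week recovery window (21 days) is longer than the 2-week limit (14 days) in Dose Delays and Dose Reductions. Beyond that limit the monitor must be consulted and patients should in general be withdrawn. The exception there covers Grade 3–4 left ventricular dysfunction, not asymptomatic falls generally.

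**The case against.** The strongest reply is that a specific rule governs a general one. Sections 5.0 and 8.0 item 2 read as summaries, the pointers above lead to the cardiac section, and an experienced investigator would follow it. The bare word for stopping is also ambiguous: elsewhere the protocol adds permanently or temporarily when it wants to be clear. The event is rare; on the figures above there is an 81–90% chance that no patient is affected.

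Much of this stands. The cardiac section is probably what was intended, and the ambiguity limits how large a difference can be claimed. It does not remove the conflict. Later text that adds a threshold is detail, but text that continues drug where the earlier sentence stops it changes the action. Even a temporary stop is incompatible with dosing until the retest.

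A reader might infer that the gap is months of dosing, by comparing a permanent stop at day 60 with a restart that runs to day 180. The documents do not support a minimum of that kind. It needs the stop to be permanent, and the 3 weeks limit recovery, not the date of restart, which waits for approval. The 2-week delay limit may intervene, and dosing after restart is at a reduced dose.

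**Conclusion.** The protocol contradicts itself for an asymptomatic LVEF fall of at least 20% to below the LLN, and the wording should be corrected. The firm difference is 7–14 days of continued dosing before the retest. Anything larger depends on whether the stop is permanent and on when a restart occurs.

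The expected count of roughly 0.1–0.2 in 30 patients rests on rates from other populations and on the assumed split between symptomatic and asymptomatic events. It should not be read as an upper bound, since scheduled echocardiograms could detect more.

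Nor should a reader infer that every small dip in LVEF is in conflict. Section 5.0 lists decreased ejection fraction among graded events, so it need not cover trivial changes. The point is confined to a fall the protocol itself calls an SAE. It concerns patient safety and consistent conduct, and no effect on the efficacy analysis is claimed.

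**What to change.** In Section 5.0 and Section 8.0 item 2, replace the ejection-fraction clause with: *LVEF decline is managed under Criteria for Evaluating Cardiac Events and the Cardiac row of Table 1, which take precedence over the grade-based rules in this section and the two-week delay limit in Dose Delays and Dose Reductions.* Also state what to do when LVEF falls below 50% without meeting the threshold of at least 20% and below the LLN. Otherwise the new wording would leave such patients with no stated action.

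If the sponsor intends the stricter rule, keep the discontinuation sentences and add an LVEF threshold. Then delete from the cardiac criteria the words that keep the patient on drug until the retest, and the restart step, with matching edits to the NYHA class I–II text in Table 1.

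The choice belongs to the sponsor and the medical monitor. The cost is a few sentences of protocol wording, with no change to sample size, visits or analysis.

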For any other NCI-CTCAE v3.0 Grade 3 or 4 adverse events or any clinically significant, lower-grade adverse event, treatment with lapatinib should be interrupted for a maximum of 14 days until the patient recovers completely or the adverse event reverts to NCI-CTCAE v3.0 Grade 1 or to baseline grade. If recurrence of adverse event after drug holiday / interruptions is observed a dose reduction by 250mg is recommended. Dose reduction should only be implemented when all supportive care measures have been exhausted without an improvement of patient status. Lapatinib should not be used at doses below 1000mg if given as monotherapy or 750mg in combination with trastuzumab. In all cases where the subject is withdrawn due to unusual or unusually severe adverse event considered related to lapatinib, the investigator must report the withdrawal as an SAE and on the CRFs.

Table 1 Summary of dose holding/interruptions and dose de-escalation recommendations for GW572016 (lapatinib) in case of lapatinib related adverse events (graded according to NCI-CTCAE v3.0)

Adverse events	Action
Non-hematological, Grade 1 or 2	Continue lapatinib therapy at full dose prescribed (see adverse events management instructions section Error! Reference source not found. Apply maximum supportive care recommendations (see Error! Reference source not found.) If prolonged duration of Grade 2 adverse event is affecting quality of life a one-time decrease of dose by 250 mg is allowed.

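### The general toxicity rules conflict for Grades 2 to 4 with no stated order of precedence, and the fifty-percent cut at Grade 3 gives 625 mg against the protocol's own 1000 mg monotherapy floor

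*Combined protocol and SAP*

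**What the plan says.** The starting dose is 1250 mg daily (Section 4.0). General toxicity rules then appear in four places.

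- **Section 5.0, Withdrawal of Subjects.** Lapatinib is discontinued in "those with toxicity greater than or equal to Grade 2 on the NCI-CTC".
- **Section 8.0, item 2.** Subjects with "toxicity less than or equal to Grade 2 on the NCI-CTC will have their dose held and resumed when the toxicity has resolved". At Grade 3 they "will have their dose held and resumed at a fifty percent dose reduction when the toxicity has resolved". Those with "toxicity equal to Grade 4 on the NCI-CTC will be discontinued on the study drug".
- **Section 8.0, Table 1** (lapatinib-related events). For non-hematological Grade 1 or 2: "Continue lapatinib therapy at full dose prescribed". It adds: "If prolonged duration of Grade 2 adverse event is affecting quality of life a one-time decrease of dose by 250 mg is allowed". For Grade 3 or 4 it holds the drug for up to 14 days until the event falls to Grade 1 or lower, with permanent discontinuation for named events.
- **Section 8.0, Other adverse events and Dose Delays and Dose Reductions.** For other Grade 3 or 4 events, or "any clinically significant, lower-grade adverse event, treatment with lapatinib should be interrupted for a maximum of 14 days". It continues: "If recurrence of adverse event after drug holiday / interruptions is observed a dose reduction by 250mg is recommended". The same paragraph sets a floor of 1000 mg for monotherapy. Dose Delays and Dose Reductions allows one reduction per subject and requires the Medical Monitor to be consulted before dosing is changed. After a Grade 3 or 4 drug-related event it also lets the investigator discuss a reduction with the Medical Monitor.

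**The concern.** An investigator whose patient has Grade 2 fatigue or anorexia can find written authority to stop the drug, to pause it, or to carry on at full dose. Whichever is chosen departs from another rule in the same protocol. The protocol calls the study a safety and activity trial and runs it at three sites, so similar patients could be managed differently with each site able to cite the text. Section 8.0, item 1, reports that most adverse events on monotherapy were Grade 1 or 2, and that is where stop, pause and continue collide. At Grade 3, the instruction to halve the dose leads to a dose that the protocol elsewhere says should not be used.

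**Working it through.** **Step 1: the rules side by side**, for a non-hematological, lapatinib-related event.

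| Grade | Section 5.0 | Section 8.0, item 2 | Table 1 and the text around it |
|---|---|---|---|
| 1 | no rule | hold, then resume | full dose; interrupt if clinically significant |
| 2 | discontinue | hold, then resume | full dose; interrupt if clinically significant; one optional 250 mg decrease if prolonged and affecting quality of life |
| 3 | discontinue | hold, then resume at half dose | hold up to 14 days; 250 mg cut recommended on recurrence, or discussed with the Medical Monitor |
| 4 | discontinue | discontinue | hold up to 14 days, except named events |

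The distinct general actions number three at Grade 2, three at Grade 3 and two at Grade 4.

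**Step 2: is there a precedence rule?** Four texts could serve.

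- The title of Section 8.0, item 1, points to detail further on. It does not say that later text prevails, and it does not reach Section 5.0.
- Medical Monitor consultation applies to a change in dosing. A site that continues at full dose changes nothing, so nothing triggers it.
- The Executive Committee in Table 1 decides only on Grade 3 or 4 events that have not resolved within two weeks.
- The DSMB monitors safety and is given no role in ranking dosing rules.

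None of them says which rule governs.

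**Step 3: the dose arithmetic.** The inputs are 1250 mg (Section 4.0), the 1000 mg monotherapy floor (Other adverse events, repeated in Table 1), 250 mg tablets (Pharmaceutical Information, How Supplied), and the one-reduction limit (Dose Delays and Dose Reductions). The protocol states no reduced dose in milligrams for the fifty-percent rule, so there is no figure of its own to reproduce.

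- Fifty-percent cut: 1250 × 0.5 = 625 mg.
- Distance below the floor: 1000 − 625 = 375 mg.
- Tablets: 625 ÷ 250 = 2.5, not a whole number.
- One 250 mg step: 1250 − 250 = 1000 mg = 4 tablets, exactly at the floor.
- Two 250 mg steps: 1250 − 2 × 250 = 750 mg, which is 1000 − 750 = 250 mg below the floor and one step over the one-reduction limit.

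The whole-tablet doses below 1250 mg are 1000, 750, 500 and 250 mg. Only 1000 mg meets the floor.

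**Step 4: what survives the most lenient reading?** Suppose that discontinuation in Section 5.0 means only a pause, with Section 8.0, item 2, supplying the resume rule. Hold against continue remains for Grade 1 and 2 events that are not clinically significant. After a first Grade 3 event that recovers, one text resumes at 625 mg, while the other calls for a cut only on recurrence or after discussion. At Grade 4, discontinuation in Section 8.0, item 2, still conflicts with the hold in Table 1.

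**The case against.** The strongest reply is that Section 5.0 need not mean a terminal stop. The cardiac criteria use discontinuation for a temporary pause followed by restart, and several event-specific rules add the word permanently where a final stop is meant. That makes the wording less certain than it first looks. A stop is still the more natural reading. The sentence stands under Withdrawal of Subjects and gives no resume rule, and Section 8.0, item 2, treats holding and discontinuing as different actions. Step 4 shows that conflicts remain either way.

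Second, the interruption for clinically significant lower-grade events lets Table 1's full-dose row be read as covering only the remaining events. That narrows hold against continue but does not remove it, because Section 8.0, item 2, holds for every toxicity of Grade 2 or lower.

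Third, diarrhea, liver, heart, lung and skin have their own sections, so the general conflict falls mainly on other events such as fatigue and anorexia. This limits the scope, although no text says that those sections override Section 5.0. A reader might infer that the unqualified stops for decreased ejection fraction and pulmonary symptoms are equally serious contradictions. The documents do not support that weight: the cardiac and lung sections give thresholds and steps, and item 1 signals that detail follows.

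Fourth, a reader might take Table 1's allowance of up to two reductions as an instruction to give 750 mg. It is a maximum to be considered, in a table that also covers combination use and repeats the 1000 mg monotherapy floor. It can be read as capped by that floor. It is inconsistent with the one-reduction limit and needs tidying.

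Finally, a 625 mg restart would go to the Medical Monitor before it happened. That is a real safeguard, but the written rule would remain wrong.

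**Conclusion.** The point stands. The general rules contradict each other at Grades 2, 3 and 4, and no text ranks them. The three-way conflict at Grade 2 assumes a non-hematological, lapatinib-related event without its own section, and reads discontinuation in Section 5.0 as a stop. The dose conflict needs neither assumption: 625 mg is 375 mg under the stated monotherapy floor and cannot be made from whole 250 mg tablets. Because following one patient-safety rule breaks another, this is an error in the text and not merely missing detail.

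A reader might go further and infer lost exposure, a given number of affected patients, or reduced power. The documents do not support such figures. They do not separate Grade 1 from Grade 2 incidence, and they do not show which rule sites would follow.

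**What to change.** 1. Delete the grade rules in Section 5.0 and Section 8.0, item 2, and refer both to Table 1 as the single governing grade table.
2. Revise Table 1 to one action per grade, reconciled with the interruption for clinically significant lower-grade events. The sponsor's clinicians and the Medical Monitor should confirm the actions for Grades 2, 3 and 4. The hematological row now directs chemotherapy, so it should state what happens to lapatinib.
3. State that the liver, cardiac, lung, skin and diarrhea sections override the table.
4. Delete the fifty-percent reduction and the allowance of up to two reductions. State that the only permitted reduction is one 250 mg step to 1000 mg, and that a Grade 2 quality-of-life decrease uses it up.
5. Leave full-dose resumption after a first recovered Grade 3 event as Table 1 now allows, unless the clinicians decide otherwise.
6. As secondary tidying, replace the unqualified ejection-fraction and pulmonary stops in Sections 5.0 and 8.0, item 2, with references to the cardiac and lung sections.

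The cost is a protocol amendment and a site letter, with no added procedures or patients.
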